### **9.2 Dose Modification for Azacitidine**

If myelosuppression is present, subsequent treatment cycles of azacitidine should be delayed until there is hematologic recover (ANC  $\geq$  1,000/ $\mu$ L, platelets  $\geq$  50,000/ $\mu$ L). Following the first cycle of azacitidine treatment, if any of the following non-hematologic toxicities are present, azacitidine treatment should not be restarted until the toxicity is resolved: 1) serum bicarbonate level  $<$  20 mEq/L, 2) serum creatinine  $\geq$  2 mg/dL; 3) SGPT, total bilirubin  $\geq$  2 times ULN; 4) and active or uncontrolled infection. Subjects will continue taking pembrolizumab on schedule if toxicity is not related to this agent.

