## 5.2. Dose Limiting Toxicities

All toxicities will be graded according to the NCI CTCAE version 4.0 and assessed for relationship to study medications.

The incidence of DLT(s) assessed in the first 6 evaluable subjects during the first 6 weeks will be to initially determine whether the dose level of combination therapy is tolerable. A subject will be considered evaluable for DLT if they have received at least 1 dose of pembrolizumab after receiving the initial week of azacitidine. DLT should not be an AE considered by the investigator to be disease related. The following drug-related AE (whether related to one or both agents) will be considered a DLT:

- Any Grade  $\geq 3$  drug-related non-hematological AE, including the following laboratory abnormalities
  - If a subject has baseline Grade  $\leq 1$  AST, ALT, or total bilirubin, a drug-related Grade  $\geq 3$  toxicity will be considered a DLT
  - If a subject has baseline asymptomatic Grade 2 AST or ALT due to tumor infiltration in the liver, drug-related elevations in AST and/or ALT  $> 2x$  baseline or a maximum of  $> 8x$  ULN that does not resolve to Grade 2 or less within 48 hours (if symptomatic) or that does not resolve to Grade 1 or less within 3 weeks of onset (if asymptomatic) will be considered a DLT.
- Any Grade  $\geq 3$  drug-related non-hematological laboratory abnormality with the following exceptions:
  - Grade 3 abnormal laboratory result that is asymptomatic and lasts no longer than 72 hours.
  - Grade 4 lymphocytopenia not associated with symptoms or clinical manifestations
- Any toxicity managed by discontinuation of pembrolizumab (see [section 9.1](#)).
- Any toxicity managed by discontinuation of azacitidine (see [section 9.2](#)).
- Grade  $\geq 3$  thrombocytopenia with bleeding, and febrile neutropenia of any Grade.

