**Table 1. Adequate Organ Function Laboratory Values**

System	Laboratory Value
Hematological	
Leukocytes	$\geq 2,000/\text{mcL}$
Absolute neutrophil count (ANC)	$\geq 1,500/\text{mcL}$
Platelets	$\geq 100,000/\text{mcL}$
Hemoglobin	$\geq 9\text{ g/dL}$ without transfusion or EPO dependency within 7 days
Renal	
Creatinine OR Measured or calculated a creatinine clearance (GFR can also be used in place of creatinine or CrCl)	$\leq 1.5 \times$ upper limit of normal (ULN) OR $\geq 60\text{ mL/min}$ for subject with creatinine levels $> 1.5 \times$ institutional ULN
Hepatic	
Total bilirubin	$\leq 2\text{ mg/dL}$ or direct bilirubin $\leq$ ULN for those with total bilirubin $> 2 \times$ ULN Subjects with Gilbert Syndrome will be eligible if total bilirubin is $< 3.0\text{ mg/dL}$ .
AST (SGOT) and ALT (SGPT)	$\leq 2.5 \times$ ULN OR $\leq 5 \times$ ULN for subjects with liver metastases
Albumin	$> 3.0\text{ mg/dL}$
Amylase and Lipase	$\leq 1.5 \times$ ULN. Subjects with Amylase or Lipase $> 1.5 \times$ ULN may enroll if there are neither clinical nor radiographic signs of pancreatitis
Coagulation	
INR or PT aPTT	$\leq 1.5 \times$ ULN unless subject is receiving anticoagulant therapy as long as PT or aPTT is within therapeutic range of intended use of anticoagulants

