### **8.2.2 Dose Modification (Escalation/Titration/Other)**

The Common Terminology Criteria for Adverse Events version 4.0 (CTCAE 4.0) must be used to grade the severity of adverse events.

If appropriate, the investigators may attribute each toxicity event to either one of the investigational agents and use stepwise dose modifications according to Table 5. Pembrolizumab dose reductions are not permitted. Pembrolizumab treatment may be interrupted or discontinued due to toxicity.

If a dose level reduction for toxicity occurs with azacitidine, the dose may not be re-escalated. Dose modifications are always based on the previous cycle.

Subjects may have up to 1 dose level reductions of azacitidine as described in Table 6. If further toxicity occurs or the criteria for resuming treatment are not met, the subject must be discontinued from treatment.

If a toxicity is not otherwise specified, investigators should refer to the label or local standard of care for dose adjustments. At the investigator's discretion, dose modification according to Table 5 is allowed for intolerable Grade 2-3 toxicities that are not specified in the tables below.

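### Section 9.2 withholds azacitidine from cycle 2 at liver-test values that Table 1 accepts at entry, with no allowance for baseline and no stated end to the hold

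*Combined protocol and SAP*

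**What the plan says.** Section 9.2 applies "Following the first cycle of azacitidine treatment". If any of four listed non-hematologic findings is present, "azacitidine treatment should not be restarted until the toxicity is resolved". The third is "SGPT, total bilirubin" at 2 × ULN or more. The limit is absolute. The section gives no baseline exception, no maximum delay, and no definition of resolution for a subject who started above the limit. It keeps the subject on pembrolizumab if the toxicity is unrelated to that drug.

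Table 1 (Section 6.1) sets the entry limits. AST and ALT (SGPT) may be up to 2.5 × ULN, with a higher limit of 5 × "ULN for subjects with liver metastases". Total bilirubin may be up to 2 mg/dL, but there are two further routes. One admits subjects whose direct bilirubin does not exceed "ULN for those with total bilirubin" above 2 × ULN. The other admits Gilbert syndrome below 3.0 mg/dL.

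Section 8.2.2 allows one azacitidine dose-level reduction. It then says that if further toxicity occurs or "the criteria for resuming treatment are not met, the subject must be discontinued from treatment".

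Two other places do make allowance for a raised baseline: the dose-limiting toxicity (DLT) definition in Section 5.2, and footnote a to Table 5 for pembrolizumab. Both use rules relative to baseline for subjects who start with Grade 2 AST or ALT.

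**The concern.** The entry rule and the restart rule use the same laboratory tests with different limits, and the restart limit is the lower one. A subject can therefore be eligible, receive cycle 1, and meet the hold criterion at cycle 2 without any change in liver tests. If the value reflects stable liver involvement, nothing in Section 9.2 says when the hold ends.

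The trial tests azacitidine priming combined with pembrolizumab in a single arm of 31. A subject held in this way has had one azacitidine cycle but still counts in the primary PFS analysis. Investigators could also handle the same subject differently: one might restart because nothing has changed, another might hold azacitidine and continue pembrolizumab, and a third might stop all treatment under Section 8.2.2. Azacitidine exposure would then depend on how the text is read.

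**Working it through.** The plan gives no figure to reproduce. The check compares intervals in multiples of ULN.

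**1. SGPT.** Held at cycle 2: 2.0 × ULN or more (Section 9.2).
- Without liver metastases, eligible up to 2.5 (Table 1). Overlap 2.0 to 2.5.
- With liver metastases, eligible up to 5.0 (Table 1). Overlap 2.0 to 5.0.

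**2. Total bilirubin.** Held at cycle 2: 2.0 × ULN or more.
- Direct-bilirubin route: total bilirubin is above 2 × ULN by definition, so every subject admitted this way lies in the hold range at entry.
- The other two routes are in mg/dL and the documents give no ULN. Assume ULN is 1.0 to 1.3 mg/dL.
  - General limit: 2/1.3 = 1.5 to 2/1.0 = 2.0 × ULN. This touches the hold limit only at the bottom of the assumed range.
  - Gilbert limit: 3.0/1.3 = 2.3 to 3.0/1.0 = 3.0 × ULN. This leaves an overlap across the whole assumed range.

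**3. Either test or both.** Section 9.2 joins the two tests with a comma only.
- If either suffices, steps 1 and 2 apply separately.
- If both are required, the overlap narrows but does not vanish. A subject with liver metastases can enter with SGPT of 2.0 to 5.0 × ULN and, by the direct-bilirubin route, total bilirubin above 2 × ULN.

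**4. Timing.** Azacitidine runs on a 28-day cycle (Table 3), so cycle 2 starts in week 5. The Trial Flow Chart takes chemistry on Day 1 of each cycle, and Section 12.1.6.7 requires acceptable results before each dose. The comparison with the 9.2 limit will therefore be made.

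**5. Place in the primary analysis.** Pembrolizumab starts in week 3 (Table 3). Section 13.1.1 counts a subject for PFS after one pembrolizumab dose; Section 15.2.3 does so after one dose of protocol therapy. Under either, a subject dosed on schedule and first held at week 5 is already in the analysis and is not replaced. Each such subject is 1/31 = 3.2% of the planned sample.

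**6. Consistency with the rest of the protocol.**
- Section 5.2, raised baseline AST/ALT: relative to baseline.
- Table 5 footnote a, raised baseline AST/ALT: relative to baseline.
- Section 9.2: absolute limit only.

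**7. What follows a hold.** Section 9.2 continues pembrolizumab when the toxicity is unrelated to it. Section 8.2.2, applied to a first hold, would end treatment. The two do not fit together unless 8.2.2 is confined to events after a dose reduction, which it does not say.

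**The case against.** **An unchanged baseline value is not a toxicity.** Section 9.2 speaks of toxicities and their resolution, and Section 10.2.4 records a preexisting condition as an adverse event only if it worsens. An investigator could reasonably conclude that a stable value does not trigger the hold. That reading is available, but Section 9.2 labels the listed absolute values as the toxicities and contains no baseline test. The allowance appears in two other sections and is absent here.

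**A stricter limit after first exposure may be deliberate.** Section 8.4 names advanced malignant hepatic tumors as a contraindication and notes higher risk with severe hepatic impairment. This is a fair point, and a lower re-treatment limit is not an error in itself. It still leaves cycle 1 given at values at which cycle 2 is withheld, with no account of what happens next.

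**A hold is not a discontinuation, and 8.2.2 may not apply.** The 8.2.2 sentence directly follows the one on dose reduction and can be read as governing only that situation. This stands, so the sentence is treated here as ambiguous and not as an automatic end of treatment.

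**A stronger inference is not supported.** Section 5.2 lists "Any toxicity managed by discontinuation of azacitidine" among DLTs, and week 5 lies inside the 6-week DLT window. A reader might infer that a baseline value would be counted as a DLT, and that two such subjects among the first six could stop the dose level. The documents do not support that. Section 5.2 confines DLTs to drug-related adverse events that are not considered disease related, and has its own baseline-relative rule for raised AST or ALT. Under Section 10.2.4 an unchanged condition is not an adverse event. A hold starting at week 5 also has no stated route in Section 9.2 to discontinuation by week 6.

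**Conclusion.** The inconsistency is real. Table 1 admits subjects at SGPT and bilirubin values at which Section 9.2, read literally, withholds azacitidine from cycle 2 onward with no stated end. The SGPT overlap is 2.0 to 2.5 × ULN, or 2.0 to 5.0 × ULN with liver metastases. The bilirubin overlap covers everyone admitted by the direct-bilirubin route, and part of the Gilbert route if ULN is 1.0 to 1.3 mg/dL. Reading the two tests as jointly required narrows the overlap without removing it.

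Only subjects still at or above 2 × ULN at week 5 are affected, not everyone who enters there. Their number, and any effect on PFS, cannot be computed, because the documents give no baseline distribution of liver tests. What can be said is that such subjects stay in the primary analysis after a single azacitidine cycle, and that the text does not settle whether they also lose pembrolizumab. The conclusion rests on the literal wording of Section 9.2; an unwritten baseline exception would remove most of it.

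**What to change.** The sponsor should reconcile Table 1 with Sections 8.2.2 and 9.2, using Section 5.2 and Table 5 footnote a as the comparison. The revised text should state:

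- how the restart limit applies to a subject who entered at or above it, including what counts as resolution for that subject;
- whether the SGPT and bilirubin criterion is met by either test or only by both;
- whether a hold for a value unchanged from baseline leads to discontinuation, and if so of azacitidine alone or of all treatment, so that Sections 8.2.2 and 9.2 agree.

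Which limit or rule is right is a clinical decision for the sponsor, and this review takes no position on it. The cost is protocol wording only; sample size, endpoint and analysis are unchanged.

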**Table 6 Dose Levels for Trial Medications**

Drug	Starting Dose	Dose Level -1	Dose Level -2
Pembrolizumab	200 mg fixed dose	No dose reductions are permitted	No dose reductions are permitted
Azacitidine	50 mg/m 	40 mg/m 	Discontinue

## **10. ADVERSE EVENTS: LIST AND REPORTING REQUIREMENTS**

### **10.1. Definition of an Overdose for this Protocol and Reporting of Overdose to Sponsor-Investigator and to Merck**

For purposes of this trial, an overdose of:

- pembrolizumab will be defined as any dose of 1,000 mg or greater ( $\geq$ 5 times the indicated dose).
- Azacitidine will be defined as any dose  $\geq$  20% over the prescribed dose.

No specific information is available on the treatment of overdose of pembrolizumab. In the event of overdose, the subject should be observed closely for signs of toxicity. Appropriate supportive treatment should be provided if clinically indicated.

There is no known specific antidote for azacitidine overdosage. In the event of an overdose of azacitidine, the patient will be monitored with appropriate blood counts and will receive supportive treatment as necessary..

If an adverse event(s) is associated with (“results from”) the overdose of a Merck product, the adverse event(s) is reported as a serious adverse event, even if no other seriousness criteria are met.

If a dose of Merck’s product meeting the protocol definition of overdose is taken without any associated clinical symptoms or abnormal laboratory results, the overdose is reported as a non-serious Event of Clinical Interest (ECI), using the terminology “accidental or intentional overdose without adverse effect.”

All reports of overdose with and without an adverse event must be reported within 24 hours to the Sponsor-Investigator and within 2 working days hours to Merck Global Safety. (Attn: Worldwide Product Safety; [contact])

## **10.2. Anticipated Adverse Events**

Pembrolizumab: Refer to [section 8.3.6](#) for specific adverse events related to pembrolizumab.

Azacitidine: The primary toxicities of azacitidine include bone marrow suppression, nausea and vomiting, diarrhea, constipation, injection site erythema, pyrexia, and ecchymosis.

## **10.3. Adverse Events Definitions:**

### **10.2.1 Adverse Event:**

An adverse event (AE) is any untoward or unfavorable medical occurrence in a human subject, including abnormal sign, symptom or disease, temporally associated with the subject’s participation in research, whether or not considered related to the subject’s participation in the research. Abnormal results of diagnostic procedures are considered to be adverse events if the abnormality:

- results in study withdrawal
- is associated with a serious adverse event
- is associated with clinical signs or symptoms
- leads to additional treatment or to further diagnostic tests
- is considered by the investigator to be of clinical significance

### **10.2.2 Serious Adverse Event:**

A serious adverse event is any adverse event occurring at any dose or during any use of the Sponsor’s product that is:

- fatal
- life-threatening
- requires inpatient hospitalization/prolongation of existing hospitalization, unless:
  - routine treatment or monitoring of the studied indication, not associated with any deterioration in condition (procedures such as central line placements, paracentesis, pain control)
  - elective or pre-planned treatment for a pre-existing condition that is unrelated to the indication under study and has not worsened since the start of study drug
  - treatment on an emergency outpatient basis for an event not fulfilling any of the definitions of an SAE given above/below and not resulting in hospital

- admissions
- social reasons and respite care in the absence of any deterioration in the patient's general condition
- results in persistent or significant disability or incapacity
- a congenital anomaly or birth defect
- an important medical event

Important medical events are those that may not be immediately life threatening, but are clearly of major clinical significance. They may jeopardize the subject, and may require intervention to prevent one of the other serious outcomes noted above. For example, drug overdose or abuse, a seizure that did not result in in-patient hospitalization or intensive treatment of bronchospasm in an emergency department would typically be considered serious.

All adverse events that do not meet any of the criteria for serious events should be regarded as non-serious adverse events.

Progression of the cancer under study is not considered an adverse event.

#### **10.2.3 Unanticipated Problem:**

An unanticipated problem is any incident, experience or outcome involving risks to subjects or others in any human subjects research that meets all of the following criteria:

- Unexpected (in terms of nature, severity or frequency) given (a) the research procedures that are described in the IRB-approval protocol and informed consent document, and (b) the characteristics of the subject population being studied;
- Related or possibly related to participation in such research (e.g., there is a reasonable possibility that the incident, experience or outcome may have been caused by the procedures involved in such research); and
- Suggests that the research places subjects or others at a greater risk of harm (including physical, psychological, economic or social harm) than was previously known or recognized.

#### **10.4. Events of Clinical Interest**

Selected non-serious and serious adverse events are also known as Events of Clinical Interest (ECI) and must be reported within 24 hours to the Sponsor-Investigator and within 2 working days to Merck Global Safety. (Attn: Worldwide Product Safety; [contact]).

For the time period beginning when the consent form is signed until treatment allocation/randomization, any ECI, or follow up to an ECI, that occurs to any subject must be reported within 24 hours to the Sponsor-Investigator and within 2 working days to Merck Global Safety if it causes the subject to be excluded from the trial, or is the result of a protocol-specified intervention, including but not limited to washout or discontinuation of usual therapy, diet, placebo treatment or a procedure.

For the time period beginning at treatment allocation/randomization through 90 days following cessation of treatment, or 30 days following cessation of treatment if the subject initiates new

anticancer therapy, whichever is earlier, any ECI, or follow up to an ECI, whether or not related to Merck product, must be reported within 24 hours to the Sponsor and within 24 hours to Merck Global Safety.

Events of clinical interest for this trial include:

- An overdose of Merck product, as defined in [Section 10.1 - Definition of an Overdose for This Protocol and Reporting of Overdose to the Sponsor-Investigator](#), that is not associated with clinical symptoms or abnormal laboratory results.
- An elevated AST or ALT lab value that is greater than or equal to 3X the upper limit of normal and an elevated total bilirubin lab value that is greater than or equal to 2X the upper limit of normal and, at the same time, an alkaline phosphatase lab value that is less than 2X the upper limit of normal, as determined by way of protocol-specified laboratory testing or unscheduled laboratory testing.\*
- **\*Note:** These criteria are based upon available regulatory guidance documents. The purpose of the criteria is to specify a threshold of abnormal hepatic tests that may require an additional evaluation for an underlying etiology.

## **10.5. Adverse Event Reporting Period**

The study period during which adverse events must be reported is normally defined as the period from the initiation of any study procedures (e.g., after the first dose of study treatment) to the end of the study treatment (e.g., last dose of study treatment) and/or follow-up. For this study, the study treatment follow-up is defined as 30 days following the last administration of study treatment, or 30 days following the decision to remove the subject from study treatment, whichever is earliest.

### **10.2.4 Baseline/Preexisting Condition**

A baseline/preexisting condition is one that is present at the start of the study. A preexisting condition should be recorded as an adverse event if the frequency, intensity, or if the character of the condition worsens during the study period.

### **10.2.5 General Physical Examination Findings**

At screening, any clinically significant abnormality should be recorded as a preexisting condition. At the end of the study, any new clinically significant findings/abnormalities that meet the definition of an adverse event must also be recorded and documented as an adverse event.

### **10.2.6 Post-study Adverse Event**

All unresolved adverse events should be followed by the investigator until the events are resolved, the subject is lost to follow-up, or the adverse event is otherwise explained. At the last scheduled visit, the investigator should instruct each subject to report any subsequent event(s) that the subject, or the subject's personal physician, believes might reasonably be related to participation in this study.

#### **10.2.7 Abnormal Laboratory Values**

A clinical laboratory abnormality should be documented as an adverse event if any one of the following conditions is met:

- The laboratory abnormality is not otherwise refuted by a repeat test to confirm the abnormality
- The abnormality suggests a disease and/or organ toxicity
- The abnormality is of a degree that requires active management (e.g., change of dose, discontinuation of the drug, more frequent follow-up assessments, further diagnostic investigation, etc.).

#### **10.2.8 Hospitalization, Prolonged Hospitalization or Surgery**

Any adverse event that results in hospitalization or prolonged hospitalization should be documented and reported as a serious adverse event unless specifically instructed otherwise in

this protocol. Any condition responsible for surgery should be documented as an adverse event if the condition meets the criteria for an adverse event.

Neither the condition, hospitalization, prolonged hospitalization, nor surgery are reported as an adverse event in the following circumstances:

- Hospitalization or prolonged hospitalization for diagnostic or elective surgical procedures for a preexisting condition. Surgery should **not** be reported as an outcome of an adverse event if the purpose of the surgery was elective or diagnostic and the outcome was uneventful.
- Hospitalization or prolonged hospitalization required to allow efficacy measurement for the study.
- Hospitalization or prolonged hospitalization for therapy of the target disease of the study, unless it is a worsening or increase in frequency of hospital admissions as judged by the clinical investigator.

